7.0 Risks

Physical Risks

Adverse events associated with oral magnesium supplementation include nausea, cramping abdominal pain, and diarrhea. These effects are caused by the osmotic action of unabsorbed magnesium salts. The magnesium supplement that has been selected for this study is magnesium glycinate. This magnesium salt readily dissolves within the intestinal tract and is less likely to cause gastrointestinal symptoms when compared to other forms of magnesium supplementation. Participants will be generally healthy and able to take all supplementation by mouth. Magnesium supplementation is not a prescribed medication, instead, it is considered a dietary supplement.

Magnesium toxicity should not occur in normal healthy subjects enrolled in this intervention trial. Excess oral intake of magnesium through dietary sources and supplement use is readily excreted by the kidneys. Magnesium supplements should be avoided in individuals with severe renal insufficiency as elevated blood levels of magnesium and toxicity can occur in these individuals. Subjects with renal insufficiency will be excluded from this investigation. Should a study subject developed acute renal insufficiency the development of magnesium toxicity is possible. However, if this were to occur it is much more likely that the study subject will present with symptoms of renal insufficiency rather than magnesium toxicity. Having said this, the oral intake of 30 g of magnesium daily can lead to metabolic alkalosis and hypokalemia. A single dose of over 400 g of magnesium can result in paralytic ileus and cardiorespiratory arrest. It is highly unlikely that any of these events will occur during the course of the study as the dosage form of the supplement is far below this amount.

Magnesium salts, especially those in antacids, may decrease the bioavailability and absorption of digoxin, chlordiazepoxide, and several antibiotics, including tetracycline, aminoquinolone and nitrofurantoin. It may also increase the absorption of dicumarol. Subjects who are on these medications will be instructed to take the study supplement at least two hours before or after one of these medications. Individuals currently receiving dicumarol will be excluded from participation in the study.

Magnesium has been widely used in clinical practice and tested in previous clinical trials; it has been well tolerated in previous clinical trials and the reported rate of adverse events has been low. No severe adverse event has been observed even when it was administered intravenously among pregnant women. On the other hand, magnesium supplementation improves insulin resistance and reduces insulin level. Growing evidence from studies conducted in Western societies has linked low intake of magnesium to insulin resistance and systemic inflammation and, thus, risk of diseases common in Western countries, such as type II diabetes, coronary heart disease, and recently colorectal cancer. Magnesium supplementation improves insulin resistance and reduces insulin level. According to data from the US National Health and Nutrition Examination Survey (NHANES), 1999-2000, 79% of US adults do not meet the Recommended Dietary Allowances (RDA) of magnesium. In our proposed study, the dose of magnesium supplementation is personalized based on the current intake ratio; thus, the dose used is generally smaller than that used in most previous studies. Each dose will not surpass the sex- and age-specific DRI for magnesium by more than 100mg/day. Furthermore, we use additional exclusion criteria to avoid potential side effects for subgroups of participants, including potential drug-magnesium interactions, providing additional assurance for the safety of participants. Our protocol enrolls patients believed to be healthy. As an alternative, participants may choose to temporarily or permanently stop supplementation if they feel a complication is unacceptable.

A possible complication of venipuncture is bleeding or the development of a small hematoma at

the point of needle insertion. Blood will be collected from the arm using standard sterile techniques and equipment, and direct pressure at the point of injection will stop this bleeding. Occasionally blood collection will cause a small hematoma, which will heal without permanent damage.

The dietary assessment (i.e., 24-hour recall), and measurement of height, weight, and body circumferences, and urine collection, present no physical risks.

Physical risks related to rectal biopsy For rectal biopsy, no fasting or bowel cleansing preparations is required. Participants are asked to have a bowel movement prior to arriving at clinic. Rectal biopsy has been used in a number of previous studies conducted by other investigators as well as one study conducted by our research nurse and our co-investigator ([name], gastroenterologist). In general, the risk is low. However, rectal biopsy may lead to rectal bleeding, infections or other complications, including severe or life-threatening complications. Any unexpected anoscopy events (> Grade 1 pain events and any other complications to the biopsies) will be recorded on an Adverse Events Form. Furthermore, we have developed a comprehensive procedure to monitor and report adverse events, prevent and treat complications.

Psychological Risks

Psychological risks could occur if participants feel manipulated or coerced by study personnel. Further risks are that participants may feel that study personnel judge participants based on reported behaviors. The likelihood of these events is very small. Informed consent is obtained before any counseling regarding the intervention, and all counselors are trained and monitored to present information in a non-judgmental manner.

Social Risks

Social risks could occur if confidentiality is violated. As well, dissemination of information obtained from genetic research has the potential of adversely affecting employability or insurability. The likelihood of such adverse events is very small, since identifying information will be rigorously protected. Only coded ID numbers will be used to label samples and other research materials.

8.0 Reporting of Adverse Events or Unanticipated Problems involving Risk to Participants or Others

Education

Across all intervention arms, participants are instructed to monitor for any signs or symptoms, including dizziness, flushing, muscle paralysis, troubled breathing, diarrhea etc. They are instructed to report these symptoms to study staff. Participants have the contact information for the Project Director and the PI. Participants receive this information verbally during the initial counseling session and each telephone monitoring call. Participants are encouraged to call or e-mail with questions or concerns, and participants may receive additional counseling to address the specific event.

Monitoring

Patient monitoring after rectal biopsy After the biopsy, the patient is monitored for thirty minutes. The CRC staff will check blood pressure and have the patient go to the restroom to check for bleeding prior to leaving the clinic. Patient is told that they can expect some blood on the tissue on the day of the biopsy. Bleeding heavier or more persistent than this should be reported. They should also report anal or lower abdominal pain, fever, a foul anal discharge, or anything else they think could be related to the biopsy. The gastroenterologists and the supporting medical team will handle emergencies. Any other problems discovered by the study team will be discussed at an appropriate level with the patient sufficient to affect referral to the patient's

gastroenterologists or primary care physician who will also be informed after written consent by the patient.

Any unexpected anoscopy events (> Grade 1 pain events and any other complications to the biopsies) will be recorded on an Adverse Events Form; information will include a description of the complication, a rating of the severity, other essential information needed to evaluate the complication, an assessment of the likelihood that the event was due to a study procedure, and a statement of action taken. All potential complications of biopsies are rated as mild, moderate, or severe. Minor problems after the procedure are handled in consultation with the gastroenterologist, and recorded in the subject's study file. If undue complications of biopsies or other procedures arise, the study will be stopped ahead of schedule. In addition, in the event of a severe or life-threatening complication, the Vanderbilt IRB will be immediately notified. Patients will continue their usual care with the physician. Telephone numbers for the PI and study director will be given to the subject. Emergencies will be handled by the gastroenterologist and supporting medical staff.

Monitoring of other adverse events Throughout the trial, we will closely monitor for adverse events through telephone calls, monitoring following a clinic visit, and questionnaire. Participants will be called the day following the rectal biopsy collection. We will call participants once a week for the first two weeks and once every two weeks thereafter, during which they are asked about dizziness, flushing, muscle paralysis, troubled breathing, diarrhea, or other discomforts or adverse effects potentially related to the intervention protocols. Our research objectives include identifying these problems, such that the value of these interventions might be assessed. Reported adverse events are recorded on an Adverse Report Form, reported to the Project Director and PI, who will contact these participants for further evaluation, and submitted to the IRB. Questionnaires are administered at baseline and each follow-up. Each questionnaire contains a list of potential symptoms, and participants report the frequency of each symptom during the prior week. Participants may write-down other symptoms that they have experienced during this period on the questionnaire, as well. Participants also are queried for changes in health status or medication use, which may lead to ineligibility and study exclusion. These questionnaires will be reviewed, and the Project director will be informed of those participants reporting any symptoms.

Adverse events will be considered as any untoward medical occurrence in a subject, even those not necessarily having a causal relationship with the study. Serious adverse events (SAEs) will be classified as untoward medical occurrences that a) result in death, b) are life threatening, c) require inpatient hospitalization, or d) result in persistent or significant disability/incapacity. All AEs will be recorded on an Adverse Event Form and graded as Mild (no limitation of usual activities), Moderate (some limitation), or Severe (inability to carry out usual activities) and attributed according to the relationship to the study intervention and/or procedures (Not related, Unlikely, Possible, Probable, or Definite). Action taken by study staff will also be recorded on the form. These forms remain as part of the participant's file. Mild events will be recorded and reviewed as they occur by the Project Director and the Principal Investigator, [name], in consultation with Drs. [name] and [name] as needed. AEs will be reviewed as a matter of course in monthly meetings of study investigators and staff. All Moderate and Severe AEs will be reported to the Vanderbilt IRB within 5 working days, and severe events will be reported to NIH within 5 working days. On the anniversary date of the initial IRB approval for investigator-initiated clinical trials, the principal investigator will submit to the Vanderbilt IRB an annual data safety and monitoring report summarizing the study's safety experience and efficacy over the preceding year and to date.

8.0 Study Withdrawal/Discontinuation

Participants may be withdrawn from the study if they are not able to provide blood, urine or rectal samples, or they are not able to take their supplements as instructed.

If the intervention proves clearly harmful, the study will be stopped ahead of schedule. Furthermore, a single life-threatening condition related to the intervention, or a single life-threatening event from biospecimen collection, would cause consideration for study termination. Moderate complications occurring in more than one subject from any protocol would likewise cause consideration for study termination.

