
This study will enroll 288 participants, 152 of whom have the GG genotype and 136 of whom have GA/AA genotype. Within the two genotype groups, a permuted-block randomization algorithm will be used to allocate the subjects into the treatment/placebo arm. These participants will be randomized to either treatment or placebo using a double-blind two-factorial (Ca/Mg intake ratio and genotype) design so that each treatment/placebo arm will contain 60 participants with the GG genotype and 60 participants with at least one A allele. (See details in Section 6.0)

Once our study is approved by Vanderbilt IRB, we will register our trial with [ClinicalTrials.gov](#) via a web based data entry system called the Protocol Registration System (PRS). Our trial will be registered in full not later than 21 days after the first patient is enrolled.

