- Chronic ischemic heart disease with unstable angina, chronic heart failure class III or IV, and myocardial infarction in the last 6 months
- Chronic diarrhea
- Type I diabetes mellitus
- Pituitary dwarfism
- Medication use
 - Current use of digoxin and licorice
 - Current use of blood anticoagulant drugs such as Dicumarol (Warfarin), Clopidogrel (Plavix), Prasugrel HCl (Effient), Ticlopidine (Ticlid), Lovenox (Enoxaparin), Fragmin (Dalteparin), Innohep (Tinzaparin), Eptifibatide (Integrilin), Tyrofiban (Aggrastat), and Abciximab (Reopro)
 - Current use of lithium carbonate therapy (Eskalith, Lithobid, Lithonate, Lithotabs, Apo-Lithium carbonate, Apo-Lithium carbonate SR, Carbolth, Duralith, PMS-Lithium carbonate, PMS-Lithium citrate)
- Individuals with a history of colon resection or colectomy due to any reason
- Individuals with any history of cancer other than non- melanoma skin cancer
- Individual with history of any organ transplantation

- Individual with history of gastric bypass due to any reason
- Individuals with any history of cancer other than non- melanoma skin cancer
- Individuals with Inflammatory bowel disease

4. PPCCT research staff will mail a recruitment letter describing study and invitation to potential participants.

- Mail eligible candidates an introductory letter from the parent study PI (Appendix B) and another introductory letter from the current study PI and the gastroenterologist (Appendix B) describing the study and inviting them to participate.
- A study project telephone number and email address are included with the recruitment letter.
- Letters will be mailed in waves such that 50% of candidates carry the GG genotype and the other 50% possess the GA or AA genotype. We will repeat this procedure with subsequent waves until 120 with the GG genotype and 120 with either the GA or AA genotype complete the study process.
- In the meanwhile the introductory letters will be sent to the potential participants by email.

5. PPCCT research staff will place a follow-up phone call (RECRUITMENT ELIGIBILITYFORM 3, Appendix B) beginning seven days after the letter is sent to answer questions, evaluate interest and determine the participants' potential eligibility.

- Attempts will be made to telephone each participant for the purposes of recruitment
 - Attempt includes leaving a message on an answering machine or with a household member to call regarding study.
- Answer questions about the study

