A randomized controlled study is one in which there are two groups, one treatment group and one control group. The treatment group receives the treatment under investigation, and the control group receives placebo. Assigning patients at random reduces the risk of bias and increases the probability that differences between the groups can be attributed to the treatment. Randomization is used to determine who will receive the magnesium supplement and who will receive placebo treatment.

This study will enroll 288 participants with colorectal hyperplastic polyp or/and adenoma, polyps free but being at high risk of colorectal polyps or cancer. 152 of whom have the GG genotype and 136 of whom have GA/AA genotype. Within the two genotype groups, a permuted-block randomization algorithm will be used to allocate the subjects into the treatment/placebo arm.

Finally, these participants will be randomized to either treatment or placebo using a double-blind two-factorial (Ca/Mg intake ratio and genotype) design so that each treatment/placebo arm will contain 60 participants with the GG genotype and 60 participants with at least one A allele.

Procedures

- The Principal Investigator will generate a list of the 288 participants, 152 of whom have the GG genotype and 136 of whom have GA/AA genotype.
- [name], the co-PI, will conduct the randomization and provide a script to randomly allocate the participants into each treatment/placebo arm within the two genotype groups.
- Each treatment/placebo arm will contain 60 participants with the GG genotype and 60 participants with at least one A allele.
- Both the participants and the study staff will be blind to randomization status until the conclusion of the study. Pharmacists are un-blinded to randomization status and treatment assignment.

Intervention Protocol

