Since the study has a 2 by 2 factorial design, we calculated the study power based on an ANOVA model which has two factors: treatment (treatment vs. placebo) and genotype (GG vs. GA and AA combined). There are 4 groups with 60 patients each by study design. At a 5% two-sided significance level, a two-way analysis of variance will have 94% power to detect the main treatment effect, the main genotype effect, and their interaction, assuming that the common

Table D3. Mean (standard deviations) for total erythrocyte magnesium among colorectal adenoma patients with a high Ca/Mg intake ratio, according to the Thr1482Ile *TRPM7* polymorphism.

TRPM7 genotype	Ca/Mg intake ratio>2.6 (placebo)
GG	5.25 ± 1.16 (n=16)
GA/AA	4.49 ± 0.50 (n=7)
GA	4.61 ± 0.40 (n=6)
AA*	3.7 ± 0.40 (n=1)

* There is only one patient possessing the AA for Ca/Mg ≤2.6; thus, no standard deviations can be estimated. We used the standard deviations for the GA genotype in the power calculation.

standard deviation is 0.830 (average of 1.16 and 0.50). In this calculation, we expect both the treated GG genotype group and the treated A allele carrier (GA and AA combined) group will have mean total erythrocyte magnesium of 5.25 mg/dL. If we conservatively use a standard deviation of 1.16, the power will be 71%. This power calculation is conducted using nQuery®, a commercial software.

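### Participants who cannot take the capsules may be withdrawn from the study itself, so week-12 primary outcomes can be lost for reasons that differ by arm, with no analysis set or missing-data method to deal with it

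*Combined protocol and SAP*

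**What the plan says.** **Withdrawal and exclusion.** Section 8.0 (Study Withdrawal/Discontinuation) gives two grounds for withdrawal from the study. The first concerns specimens: "Participants may be withdrawn from the study if they are not able to provide blood, urine or rectal samples". The second, in the same sentence, concerns adherence to the capsules: "or they are not able to take their supplements as instructed". Section 6.0 G (Data and Safety Monitoring Plan) adds that moderate adverse events may require temporary or permanent removal from the study. Under monitoring of other adverse events, both Section 6.0 G and Section 8.0 (Reporting of Adverse Events) say that participants are asked about "changes in health status or medication use, which may lead to ineligibility and study exclusion".

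**Numbers.** Section 5.0: "This study will enroll 288 participants, 152 of whom have the GG genotype and 136 of whom have GA/AA genotype". Sections 5.0 and 6.0 E also say that "each treatment/placebo arm will contain 60 participants with the GG genotype and 60 participants with at least one A allele". The power paragraph of Section 9.0 uses "There are 4 groups with 60 patients each by study design". Section 6.0 A describes each arm as having at least 120 participants. For invitation letters, Section 6.0 B (procedure A, step 4) repeats the waves "until 120 with the GG genotype and 120 with either the GA or AA genotype complete the study process".

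**Analysis.** Sections 6.0 I and 9.0 give t-tests or non-parametric tests within genotype and a two-way ANOVA or ANCOVA. Neither states who is analysed, what happens to people who stop capsules, or how missing week-12 values are handled. No attrition rate is given. Section 6.0 G says only that drop-out is expected to be low.

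**The concern.** Randomisation makes the arms comparable at week 0. They stay comparable at week 12 only if the people with outcomes are still a fair sample of each arm. Here the conduct rules permit removal for tolerance, adherence, adverse events and changed health or medication. All of these arise after randomisation, and some can be caused by the capsules. Section 7.0 lists nausea, abdominal cramping and diarrhoea as effects of oral magnesium. Section 6.0 G rules out a run-in, so intolerance first shows after allocation.

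The primary endpoints (TUNEL, Bax, TRPM7, COX-2, Ki-67, pMLKL) are measured in rectal tissue at week 0 and week 12. Someone withdrawn before week 12 normally has no second biopsy and cannot enter the ANOVA. This goes beyond a missing intention-to-treat sentence: if the rules are applied, the data are never collected, and no later choice of analysis set can recover them. At stake is whether an arm difference reflects magnesium or reflects who remained.

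**Working it through.** **1. The plan's own power figure.** Inputs from Section 9.0: placebo means 5.25 (GG) and 4.49 (GA/AA) mg/dL, treated mean 5.25 in both, SD 0.830 or 1.16, 60 per cell, two-sided 5%.

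- Main effect = [(5.25 − 5.25) + (5.25 − 4.49)]/2 = 0.38.
- SE = SD × √(2/120). At SD 0.83 this is 0.107.
- Power = Φ(0.38/0.107 − 1.96) = 94.4% (noncentral F with 1 and 236 df: 94.2%). The plan states 94%.
- At SD 1.16: 71.8% (noncentral F: 71.5%). The plan states 71%.

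The stated power reproduces at exactly 240 people with data. The arithmetic is sound, so this point is not a sample-size error.

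**2. The gap between 288 and 240.**

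| | Enrolled | 60-per-cell total | Gap |
|---|---|---|---|
| GG | 152 | 120 | 32 (21.1%) |
| GA/AA | 136 | 120 | 16 (11.8%) |
| All | 288 | 240 | 48 (16.7%) |

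Randomising 152 and 136 in a 1:1 ratio gives cells of 76 and 68, not 60. The documents do not explain the 48. Some may be people found ineligible from the creatinine or pregnancy samples taken at visit 1 (Section 6.0 B, steps 8–9; Section 6.0 F, Clinic Visit #1, step 5). Those samples come from the baseline visit, so that loss should not depend on arm. If 288 and 240 are read as enrolled and analysed, 16.7% is at most an upper bound on treatment-related loss.

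**3. Size of bias under stated assumptions.** Let d be the proportion lost in an arm, and let those lost be k SD worse than those who stay. The arm's true mean is μ = (1 − d)·m + d·(m − k), where m is the mean among those who stay, so m = μ + d·k. The difference among those observed is then off by

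bias = k × (d_magnesium − d_placebo)

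with k the same in both arms. If k differs by arm, bias = k_M·d_M − k_P·d_P, so equal loss rates alone do not guarantee zero bias.

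With a true effect of zero and 120 per arm, SE = √(2/120) = 0.129 SD, and type I error = Φ(−1.96 + bias/SE) + Φ(−1.96 − bias/SE).

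| Assumed loss, magnesium / placebo | k | Bias (SD) | Type I error |
|---|---|---|---|
| 16.7% / 16.7% | any | 0 | 5.0% |
| 20% / 13.3% | 0.5 | 0.033 | 5.8% |
| 20% / 13.3% | 1.0 | 0.067 | 8.1% |
| 25% / 8.3% | 0.5 | 0.083 | 9.9% |
| 25% / 8.3% | 1.0 | 0.167 | 25.2% |

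The splits and the values of k are assumptions and have no source in the documents. All rows use the full 16.7% total loss, which step 2 treats as an upper bound. The plan gives no effect size for the mucosal endpoints, so the bias cannot be set against a planned effect on them.

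**The case against.** **What stands on the other side.** The withdrawal wording is permissive. Section 6.0 E provides symptomatic treatment and stepwise reduction for diarrhoea, and Section 7.0 already mentions stopping supplements temporarily or permanently, so not everyone with side effects would be lost. Drop-out is expected to be low. Enrolling more people than the power calculation needs is ordinary practice. These points limit the likely size. They do not remove the rules that allow withdrawal, and they do not supply the missing analysis set.

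**Stronger readings that a reader might infer, and that the documents do not support:**

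- *The analysis is restricted to completers.* Neither Section 6.0 I nor Section 9.0 says so. The slide workload in the quality control text fits 240 people (240 × 2 visits × 3 sections = 1440 H&E slides), but this is weak evidence. The 7200 biomarker slides equal 240 × 2 × 3 × 5 markers, while the slide preparation text lists six stains, so the figure does not match the current marker list.
- *The plan intends to lose 48 randomised people.* No text calls the 48 a planned loss. Section 6.0 A makes 120 per arm a minimum, and the uneven gap by genotype is an odd pattern for a simple attrition allowance.
- *Recruiting until 240 complete creates the bias.* That target governs letter waves by genotype, not by arm, and later entrants are themselves randomised. Missing outcomes create the bias. Closing recruitment at a fixed number would not remove it.

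**Conclusion.** The concern holds as a risk of bias. The plan permits removal from the study for post-randomisation reasons that magnesium can cause. The primary outcome is then usually missing, and nothing is prespecified for that case. The direction and size cannot be found from the documents. Bias is zero if the two arms lose equal numbers of similar people. It is 0.03 to 0.07 SD under an assumed 20%/13% split and 0.08 to 0.17 SD under an assumed 25%/8% split, both with those lost 0.5 to 1.0 SD worse. Only the wider split raises the type I error much, to about 10% to 25%. These are illustrations and not forecasts, and nothing in the plan shows that people who cannot tolerate capsules have worse mucosal markers. The 94% power figure is not in dispute. The point should be fixed, because the remedy is cheap during conduct and unavailable afterwards.

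**What to change.** 1. **Withdrawal text** (Section 6.0 G, Section 8.0 Reporting of Adverse Events, Section 8.0 Study Withdrawal/Discontinuation): separate stopping capsules from leaving the study. Leave the rules on when capsules are reduced or stopped as they are. People who stop or miss capsules stay in follow-up and are asked for the already scheduled week-12 samples, subject to consent and to the investigator's safety judgement on biopsy.
2. **Analysis text** (Sections 6.0 I and 9.0): define the primary analysis as all randomised participants with a week-12 value, by assigned arm and genotype stratum, regardless of adherence. Because this still omits people without a value, prespecify a missing-data sensitivity analysis that covers them, such as multiple imputation. Any completer or adherer analysis is supportive. Report losses and reasons by arm.
3. **Numbers** (Sections 5.0, 6.0 E and 9.0): reconcile 288 (152/136) with 60 per cell, state the attrition assumed, and say how people found ineligible from visit 1 laboratory results are counted.

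**Cost.** The change is wording, plus attendance by non-adherent participants at one visit that is already scheduled. The effect estimate may be slightly diluted. As an illustration on erythrocyte magnesium, if all 288 give values (cells 76/76/68/68), power is 97.2% with the full effect and 93.6% with an assumed 10% dilution (SD 0.83), or 79.0% and 70.2% (SD 1.16). If only 240 give values, 10% dilution leaves 88.9% (SD 0.83) or 62.3% (SD 1.16).
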